## **7.5 SECONDARY ENDPOINT(S)**

### **7.5.1 Key secondary endpoint(s)**

This section is not applicable as no key secondary endpoint has been specified in the protocol.

### **7.5.2 Secondary endpoint(s)**

#### **7.5.2.1 mMRC**

The secondary endpoint of mMRC score, will be summarized descriptively. The percentage of patients in each dyspnoea component of mMRC instrument will be presented in absolute and relative frequencies based on the available information at each study visit. In addition, shift tables will be provided for mMRC to compare a subject's baseline evaluation relative to the visit's observed value. For all shift tables, data will be summarized as observed, ie no imputation on missing data.

Change from baseline in mMRC score is defined as post baseline – baseline value, assuming that both time points are non missing.

For the statistical inference regarding mMRC a MMRM assuming data to be missing at random will be fit. The dependent variable will be the mMRC score at each visit. Visit, GAPBSL stage, FVCBSL (cut off  $\leq 70\%$ ), DLCOBSL (cut off  $<40\%$ ) and number of

comorbidities (as dictated by the medical history page) will be entered as fixed factors, baseline score by visit as interaction term. Patients will be fitted at random and an unstructured correlation matrix will be used, allowing adjustment for correlations between study visits within the patients. In case of no convergence, the methods proposed at [Section 7.4.1](#) may be introduced.

Summaries of the estimated mean change from baseline of mMRC until months 3, 6, 9 and 12 will be provided with the corresponding 95% confidence interval. Model information will be provided as footnote under the corresponding table.

#### 7.5.2.2 Cough Visual Analogue Scale (VAS)

The secondary endpoint of cough VAS reflecting the cough burden will be summarized descriptively as continuous variables at each study visit. The VAS values to be displayed in the summaries will be the observed values at each visit and the absolute change from baseline at each visit.

Change from baseline is defined as post baseline – baseline value, assuming that both time points are non missing.

For the statistical inference regarding VAS, a mixed model for repeated measurements model (MMRM) assuming random missingness will be fitted. The dependent variable will be the VAS score at each visit. Visit, GAPBSL stage, FVCBSL (cut off  $\leq 70\%$ ), DLCOBSL (cut off  $< 40\%$ ) and number of comorbidities (as dictated by the medical history page) will be entered as fixed factors, baseline score by visit as interaction term. Patients will be fitted at random and an unstructured correlation matrix will be used, allowing adjustment for correlations between study visits within the patients. In case of no convergence, the methods proposed at [Section 7.4.1](#) may be introduced.

Summaries of the estimated mean change from baseline of VAS until months 3, 6, 9 and 12 will be provided with the corresponding 95% confidence interval. Model information will be provided as footnote under the corresponding table.

#### 7.5.2.3 GAD 7

The secondary endpoint of GAD7 reflecting severity of anxiety will be summarized descriptively as continuous variables at each study visit. The GAD 7 values to be displayed in the summaries will be the observed values at each visit and the absolute change from baseline at each visit.

Change from baseline is defined as post baseline – baseline value, assuming that both time points are non missing.

GAD-7 total score for the seven items ranges from 0 to 21. Scores of 5, 10, and 15 represent cut points for mild, moderate, and severe anxiety, respectively. Frequency of patients with mild, moderate, or severe anxiety will be displayed at each visit.

For the statistical inference regarding GAD 7 score, a mixed model for repeated measurements model (MMRM) assuming random missingness will be fitted. The dependent variable will be the GAD 7 score at each visit. Visit, GAPBSL stage, FVCBSL (cut off  $\leq 70\%$ ), DLCOBSL (cut off  $\leq 40\%$ ) and number of comorbidities (as dictated by the medical history

page) will be entered as fixed factors, baseline score by visit as interaction term. Patients will be fitted at random and an unstructured correlation matrix will be used, allowing adjustment for correlations between study visits within the patients. In case of no convergence, the methods proposed at [Section 7.4.1](#) may be introduced.

Summaries of the estimated mean change from baseline of GAD 7 score until months 3, 6, 9 and 12 will be provided with the corresponding 95% confidence interval. Model information will be provided as footnote under the corresponding table.

#### 7.5.2.4 SMAQ

The secondary endpoint of SMAQ reflecting treatment adherence will be summarized descriptively at each visit in TS. Absolute and relative frequencies of adhered / non- adhered to treatment patients will be displayed at each visit.

The questionnaire is dichotomic (yes, no), any answer in the sense of non-adherent groups, assigns patient to the non-adherent category. Thus, patient is considered non-adherent if the answers to the SMAQ questionnaire (see [Table 7.5.2.4:1](#)) are the following:

- 1: YES.
- 2: No
- 3: YES
- 4: YES
- 5: C, D or E
- 6: i) more than two days.  
ii) More than four days

Table 7.5.2.4:1 SMAQ Questionnaire

1. Do you ever forget to take your medication for IPF? Y/N
2. Do you always take your medication for IPF at the indicated time? Y/N
3. Sometimes if you feel worse, do you stop taking your medication for IPF? Y/N
4. Did you miss any of your medication for IPF last weekend? Y/N
5. Think on the last week. How often did you miss to take your medication for IPF? A: Never B: 1 - 2 C: 3 - 5 D: 6 - 10 E: >10
6. i) How many days have you missed taking your medication for IPF during the past 3 months? 6. ii) How many days have you missed one of the two daily medication for IPF doses during the past 3 months?

#### 7.5.2.5 LTOT use

The percentage of TS patients that used LTOT at each visit and the percentage of TS patients that used LTOT at least once during the study will be displayed. Percentages will be based on the number of patients with available information.

Additionally, based on the total number of visits performed from all study patients, the percentage of visits that LTOT was used will be calculated (100 x Total number of study visits that LTOT was used over the total number of study visits).

## **7.7 EXTENT OF EXPOSURE**

Only descriptive statistics are planned for this section of the report.

## **7.8 SAFETY ANALYSIS**

All safety analyses will be performed on the TS.

### **7.8.1 Adverse events**

All treatment emergent adverse events recorded during the trial will be presented in listings for AEs / SAEs. Especially the Adverse Drug Reactions (ADR), these might be followed up after the study completion and until they are resolved.

As treatment emergent adverse events are considered all the AEs following ICF signature providing the patient has already received treatment with Nintedanib.

Initially, an AE overview table will be created summarizing the total number of AEs and patients with at least one: AE, SAE, SAE leading to death, SAE leading to drug discontinuation.

A separate table showing the overview of AE occurred during the study will be presented by SOC and PT. SOC terms will be sorted alphabetically; PTs will be sorted within each SOC term by decreasing frequency. In such tables if a subject reported more than one AE within the same PT or SOC, the subject will be counted only once for this PT/SOC.

AEs will be coded based on the MedDRA terminology. The existing version at the time of the database lock will be used. For further details on summarization of AE data, please refer to (3).

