## **11. MANAGEMENT AND REPORTING OF ADVERSE EVENTS/ADVERSE REACTIONS**

### **11.1 DEFINITIONS OF ADVERSE EVENTS**

#### Adverse event

An adverse event (AE) is defined as any untoward medical occurrence in a patient or clinical investigation subject administered a medicinal product and which does not necessarily have a causal relationship with this treatment. An adverse event can therefore be any unfavorable and unintended sign (e.g. an abnormal laboratory finding), symptom, or disease temporally associated with the use of a medicinal product, whether or not considered related to the medicinal product.

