#### Serious adverse event

A serious adverse event is defined as any AE which

- results in death,
- is life-threatening,
- requires in-patient hospitalization, or
- prolongation of existing hospitalization,
- results in persistent or significant disability or incapacity, or
- is a congenital anomaly/birth defect.

Life-threatening in this context refers to a reaction in which the patient was at risk of death at the time of the reaction; it does not refer to a reaction that hypothetically might have caused death if more severe.

Medical and scientific judgement should be exercised in deciding whether other situations should be considered serious reactions, such as important medical events that might not be immediately life threatening or result in death or hospitalization but might jeopardize the patient or might require intervention to prevent one of the other outcomes listed above. Examples of such events are intensive treatment in an emergency room or at home for allergic bronchospasm, blood dyscrasias or convulsions that do not result in hospitalization or development of dependency or abuse. Any suspected transmission via a medicinal product of an infectious agent is also considered a serious adverse reaction.

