#### Collection of AEs

The study design is of non-interventional nature and the study is conducted within the conditions of the approved marketing authorization. Sufficient data from controlled interventional trials are available to support the evidence on the safety and efficacy of the studied BI drug. For this reason, the following AE collection and reporting requirements have been defined.

The following must be collected by the investigator in the (e)CRF from signing the informed consent onwards until the end of the study:

- all adverse drug reaction (ADRs) (serious and non-serious),
- all AEs with fatal outcome,

All ADRs, including those persisting after study completion must be followed up until they are resolved, have been sufficiently characterized, or no further information can be obtained.

The investigator carefully assesses whether an AE constitutes an ADR using the information below.

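### The SAP's AE and SAE tables carry all-cause labels although only ADRs and fatal AEs must be entered; the visible overview has no ADR row and counts discontinuation for SAEs only

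*SAP*

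**What the plan says.** **SAP 7.8.1** sets the scope of the listings: "All treatment emergent adverse events recorded during the trial will be presented in listings for AEs / SAEs". It defines treatment emergence by timing and exposure alone: "As treatment emergent adverse events are considered all the AEs following ICF signature providing the patient has already received treatment with Nintedanib". It then plans an overview table "summarizing the total number of AEs and patients with at least one: AE, SAE, SAE leading to death, SAE leading to drug discontinuation" and, in addition, "A separate table showing the overview of AE occurred during the study will be presented by SOC and PT". ADRs are mentioned in this section once, in a sentence about following them up after study completion. For further detail on summarising AEs the section points to reference (3), an internal sponsor guideline.

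**Protocol 11.1** defines an adverse event as any untoward occurrence, "whether or not considered related to the medicinal product". Seriousness builds on that: "A serious adverse event is defined as any AE which" meets one of the listed criteria, death among them.

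**Protocol 11.2** (Collection of AEs) narrows what has to reach the database. It cites the non-interventional design and the controlled trial evidence already available, and continues: "For this reason, the following AE collection and reporting requirements have been defined". The list is introduced by "The following must be collected by the investigator in the (e)CRF from signing the informed consent onwards until the end of the study" and has two items: all ADRs, whether serious or not, and all AEs with a fatal outcome. The expedited reporting table in the same section covers the same events, plus pregnancy forms.

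**Protocol 9.3.3, Table 1** lists the reason for treatment discontinuation as a variable at the final visit.

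**The concern.** The table labels and the collection rule do not describe the same set of events. Someone who sees a row for patients with at least one SAE, and knows the protocol's definition, will read it as all-cause. A non-fatal hospitalisation judged unrelated to nintedanib is an SAE under Protocol 11.1, yet no site is required to enter it. The same holds for the AE row and for the table by organ class and preferred term.

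ADRs are the class that the protocol does require in full, and the visible overview does not show them as such.

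The discontinuation row has a separate gap. Under Protocol 9.2.4, permanent discontinuation ends follow-up, with AEs given as one example of a reason and no restriction to serious ones. A patient who stops because of a non-serious ADR appears in the AE row, but not in the only row about stopping treatment. At stake is how the safety tables are read and how well they account for early exits.

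**Working it through.** There is no figure in the plan to reproduce. The check compares each planned output with the mandatory collection list in Protocol 11.2.

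| SAP 7.8.1 output | Meaning under Protocol 11.1 | Content under mandatory collection | Result |
|---|---|---|---|
| Any AE; total AEs | all-cause | ADRs + fatal AEs | non-fatal unrelated AEs not systematically captured |
| Any SAE | all-cause serious | serious ADRs + fatal AEs | non-fatal unrelated SAEs not systematically captured |
| SAE leading to death | all-cause fatal | all fatal AEs | complete |
| SAE leading to discontinuation | serious only | serious events only | non-serious ADRs that end treatment not counted |
| Organ class / preferred term | all-cause | ADRs + fatal AEs | same gap as the AE row |
| Any ADR; serious ADR | – | collected in full | no visible row |

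**Could other passages widen the collection?** Three use broader wording. Protocol 11.2 opens by requiring records of all AEs, but in the patient files, not the eCRF. Table 2 of Protocol 9.4 has an AE collection line at every visit. Protocol 9.2.4 says withdrawing patients should be asked about any adverse events. None replaces the mandatory list, and Protocol 9.3.3 sends the reader to Section 11.2 for AE collection. Their practical effect is that some unrelated non-fatal events may be entered, depending on the site. That makes the AE and SAE rows a mixture whose composition is unknown.

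**Can the ADR counts be recovered from the rows that exist?** Partly. Let N(SAE) be the patients with any SAE and N(death) those with an SAE leading to death. If sites enter only what is mandatory, every patient in the SAE row who is not in the death row had a serious ADR, and those in the death row may or may not have had one. So

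N(SAE) − N(death) ≤ N(serious ADR) ≤ N(SAE),

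and likewise N(AE) − N(death) ≤ N(ADR) ≤ N(AE). Once optional entries are present, the lower bounds no longer hold, because a patient can then be in the AE or SAE row with an unrelated non-fatal event only.

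**Direction of the gap.** Events outside the mandatory list can only be missing, not over-counted. Read as all-cause incidence, the AE, SAE and organ-class figures are therefore at or below the true value. The documents give neither the share of events that are non-fatal and unrelated nor the share of those that sites would enter, so no size follows.

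**The case against.** The case for leaving the text alone is substantial.

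- **The tables are not wrong.** The SAP speaks of recorded events, and nowhere calls its counts all-cause incidence. It assumes that the reader knows the protocol, where the collection rule is plain. Protocol 9.7 promises only listings and MedDRA coding, so the SAP already goes further. This stands: the defect is one of labels and missing rows, not a miscount.
- **Deaths are covered.** All fatal AEs are collected whatever their cause, a fatal AE is an SAE by definition, and SAP 7.8.5 adds a table of fatal events with the reason of death. No new fatal-event row is needed.
- **Serious ADRs are partly recoverable**, as the bounds above show, and every treatment-emergent event will be listed. This stands, but a listing is not a count and the bounds rest on there being no optional entries.
- **Unseen text may close the gap.** Reference (3) covers the presentation of AE data, and parts of the SAP are redacted. A reader might infer that ADRs will go unsummarised. The documents do not support that; they show only that the visible text of SAP 7.8.1 has no such row.
- **Safety is not a study objective**, the study is not a PASS, and no events of special interest are defined. This limits the weight of the point.

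A reader might also be tempted to size the discontinuation gap from Protocol 9.5: 240 − 200 = 40 early leavers, or 0.20 × 240 = 48 at the upper stated dropout rate. Those figures cover departures for every reason, including consent withdrawal and loss to follow-up, and nothing in the documents splits them by reason. They are not an estimate of patients who stop for a non-serious ADR.

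**Conclusion.** The point holds, as a minor one. On the visible text, all-cause labels sit on data whose mandatory content is ADRs plus fatal AEs, with other events entered unevenly if at all. Read as all-cause incidence, the AE, SAE and organ-class figures tend to be too low by an amount that cannot be estimated from the documents. The death row is complete. The overview shows no ADR count and leaves non-serious ADRs out of its only discontinuation row, although the data for both are collected.

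This rests on two assumptions: that Protocol 11.2 governs eCRF entry, as Protocol 9.3.3 indicates, and that neither reference (3) nor redacted text already supplies the rows. No primary or secondary endpoint estimate changes.

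**What to change.** In SAP 7.8.1:

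1. Add overview rows for any ADR, for serious ADR, and for ADR of any seriousness leading to permanent discontinuation of nintedanib. Keep the existing death row.
2. Present the organ class and preferred term table for ADRs and fatal AEs. Show any other recorded AEs separately, or flag them as not systematically collected.
3. Add a footnote to the AE tables stating the collection rule of Protocol 11.2.

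If reference (3) already provides some of these rows, naming them in the SAP is enough.

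The cost is a few table rows and a footnote. No new data are needed: ADRs and the reason for discontinuation are already collected, and the planned SAE discontinuation row already presumes that an event can be linked to stopping treatment.

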### **7.8.2 Laboratory data**

No laboratory data for safety evaluation will be collected.

### **7.8.3 Vital signs**

Systolic and Diastolic Blood pressure (mmHg), heart rate (bt/min) and weight (kg) will be summarized descriptively at each visit.

#### **7.8.4 ECG**

No ECG data for safety evaluation will be collected.

#### **7.8.5 Others**

The number and percentage of patients with IPF symptoms will be summarized at each study visit.

A separate table illustrating the number and percentage of patients with fatal event, the reason of death as well as the median survival time of the patients will be given. Survival time (in weeks) will be calculated as follows.

Survival time = (Date of death-FU – ICF date) / 7

A Kaplan Meier curves will display the survival distribution curve. Dates will be cut at the last time of follow up or death.

## **10. HISTORY TABLE**

Table 10: 1    History table

Version	Date (DD-MMM-YY)	Author	Sections changed	Brief description of change
1	01-APR-2020	[REDACTED]	None	This is the final TSAP
